9.5.7.1 Adverse Events

An adverse event (AE) is any untoward medical occurrence in a patient or clinical investigation subject administered an investigational product. An AE does not necessarily have a causal relationship with the medicinal product. For this study, the study drug(s) is/are lenvatinib, or lenvatinib combination regimen, or any other comparator therapy (except placebo) as per the parent study.

AEs collected in this study must be treatment-emergent adverse events (TEAE). This is defined as an AE that emerges during treatment in the roll-over study, having been absent before the time the subject signs the roll-over study ICF or

- Re-emerges during treatment in the roll-over study, having been present before signing the ICF but stopped before signing the ICF, or
- Worsens in severity during treatment in the roll-over study relative to the pre-ICF state, when the AE is continuous.

The criteria for identifying TEAEs in this study are:

- Any unfavorable and unintended sign (including an abnormal laboratory finding), symptom, or disease temporally associated with the use of an investigational product, whether or not considered related to the investigational product
- Any new disease or exacerbation of an existing disease.

- Any deterioration in nonprotocol-required measurements of a laboratory value or other clinical test (eg, ECG or x-ray) that results in symptoms, a change in treatment, or discontinuation of study drug
- Recurrence of an intermittent medical condition (eg, headache) not present pretreatment (Baseline)
- An abnormal laboratory test result should be considered a TEAE if the identified laboratory abnormality leads to any type of intervention, withdrawal of study drug, or withholding of study drug, whether prescribed in the protocol or not

A laboratory result should be considered by the investigator to be a TEAE if it:

- Results in the withdrawal of study drug
- Results in withholding of study drug pending some investigational outcome
- Results in an intervention, based on medical evaluation (eg, potassium supplement for hypokalemia
- Results in any out-of-range laboratory value that in the investigator's judgment fulfills the definitions of a TEAE with regard to the subject's medical profile

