9.7.1.8 Adverse Events

The AE verbatim descriptions (investigator terms from the CRF) will be classified into standardized medical terminology using the Medical Dictionary for Regulatory Activities (MedDRA). Adverse events will be coded to the most recent MedDRA lower level term (LLT) closest to the verbatim term. The linked MedDRA preferred term (PT) and primary system organ class (SOC) are also captured in the database.

A treatment-emergent adverse event (TEAE) is defined as an AE that emerges during treatment in the roll-over study, having been absent before the time the subject signs the roll-over study ICF or

- Re-emerges during treatment in the roll-over study, having been present before signing the ICF but stopped before signing the ICF, or
- Worsens in severity during treatment in the roll-over study relative to the pre-ICF state, when the AE is continuous.

All TEAEs will be presented in subject data listings.

An overview table, including the incidence of and the number of subjects with TEAEs, SAEs, deaths, and those TEAEs that led to study drug discontinuation, or dose interruption will be provided. The number (percentage) of subjects with TEAEs will also be summarized by relationship to study drug (Yes [related] and No [not related]). The number (percentage) of subjects with TEAEs will also be summarized by relationship to study drug (Yes [related] and No [not related]).

For the TEAEs, the incidence, severity, duration and timing in relation to the start of study medication will be summarized.

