Cohort A: Subjects who received lenvatinib monotherapy or who crossed over from a comparator arm to receive lenvatinib monotherapy in their parent study will continue to receive lenvatinib monotherapy.

Cohort B: Subjects who received lenvatinib combination therapy or who crossed over from a comparator arm to receive lenvatinib combination therapy in their parent study will continue to receive lenvatinib combination therapy.

Cohort C: Subjects who received comparator treatment in their parent study will continue to receive comparator treatment, with the exception of subjects receiving placebo. Subjects who received placebo in their parent study and who were either not permitted to cross over or who opted not to cross over to active treatment will not be eligible to enroll in this study.

Treatment Phase:

During the Treatment Phase, subjects still on treatment will continue the same treatment they received upon discontinuation of the parent study. Subjects will remain on treatment in consecutive cycles as per the parent study protocol until disease progression, development of unacceptable toxicity, subject request, withdrawal of consent, discontinuation of Study E7080-G000-604 by the sponsor, use of non-permitted concomitant drugs, unacceptable noncompliance with the protocol, or if the subject is lost to follow-up.

This is a rollover open-label study with no control group. Subjects will enter the study at the same doses of study drug of lenvatinib or the combination regimen, or any other comparator therapy (except placebo), upon discontinuation of the parent study.

Discontinuation criteria are as follows: progression of disease, unacceptable toxicity, subject request, withdrawal of consent, termination of study by sponsor, use of non-permitted concomitant drugs, unacceptable non-compliance with the protocol, subject lost to follow-up. Subjects will be permitted to continue study drug(s) beyond initial disease progression as long as the treating investigator considers that there is continued clinical benefit after discussing with the sponsor and if the subject is tolerating the study drug(s).

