6.2.2 Subject Disposition

The number of subjects enrolled, treated, and prematurely discontinued from study treatment will be summarized. The reason for study drug discontinuation will be summarized according to the categories in the eCRF.

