6.5.2 Adverse Events

The adverse event (AE) verbatim descriptions (investigator terms from the eCRF) will be classified into standardized medical terminology using the Medical Dictionary for Regulatory

Activities (MedDRA). The linked MedDRA preferred term (PT) and primary system organ class (SOC) are also captured in the database.

AEs collected in this study must be treatment-emergent adverse events (TEAE). This is defined as an AE that emerges during treatment in the rollover study, having been absent before the time the subject signs the rollover study ICF or

- Re-emerges during treatment in the rollover study, having been present before signing the ICF but stopped before signing the ICF, or
- Worsens in severity during treatment in the rollover study relative to the pre-ICF state, when the AE is continuous.

Only those AEs that are treatment emergent will be included in summary tables. TEAEs are those occurring on or after the first dose date of study drug and on or before 28 days after the last dose of study drug. All TEAEs will be presented in subject data listings.

An overview table, including the number and percentage of subjects with TEAEs, SAEs, deaths, and those with TEAEs that led to study drug discontinuation, interruption, or dose reduction will be provided. The number (percentage) of subjects with TEAEs will be summarized by SOC and PT, by relationship to study drug (Yes [related] and No [not related]), and by CTCAE toxicity grade as follows:

- Overview of TEAEs
- TEAEs by SOC and PT
- TEAEs by decreasing frequency of PT
- TEAEs with CTCAE Grade ≥ 3 by decreasing incidence of PT
- Treatment-emergent serious AEs by decreasing incidence of PT
- Overview of treatment-related TEAEs
- Treatment-related TEAEs by SOC and PT
- Treatment-related TEAEs by decreasing frequency of PT
- Treatment-related TEAEs with CTCAE Grade ≥ 3 by decreasing incidence of PT
- Treatment-related treatment-emergent serious AEs by decreasing incidence of PT
- Fatal TEAEs by decreasing incidence of PT
- TEAEs leading to treatment discontinuation of lenvatinib

The following listings will be provided for the subjects in the Safety Analysis Set:

- Demographics

- Disposition
- Lenvatinib dosing
- All AEs
- All SAEs
- Adverse events with CTCAE Grade 3 or above
- All AEs leading to study drug discontinuation
- All fatal AEs

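### The SAP's only dedicated table of TEAEs leading to discontinuation, and its only dosing listing, cover lenvatinib alone, although study drug(s) include combination partners and comparators

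*SAP*

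**What the plan says.** SAP 6.5.2 lists 12 tables of treatment-emergent adverse events. The last, and the only one devoted to discontinuation, is "TEAEs leading to treatment discontinuation of lenvatinib". It then introduces 8 listings with the words "The following listings will be provided for the subjects in the Safety Analysis Set". The only one about dosing is "Lenvatinib dosing".

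On which drugs count, protocol 9.5.7.1 says that "the study drug(s) is/are lenvatinib, or lenvatinib combination regimen, or any other comparator therapy (except placebo"), following the parent study. SAP 4.2 keeps all three cohorts. Cohort B continues lenvatinib combination therapy. For Cohort C it says: "Subjects who received comparator treatment in their parent study will continue to receive comparator treatment".

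Other SAP outputs use wider wording. Section 6.5.2 also plans the listing "All AEs leading to study drug discontinuation" and an overview row for subjects whose TEAEs led to discontinuation, interruption or dose reduction of study drug. Section 6.2.2 says: "The reason for study drug discontinuation will be summarized according to the categories in the eCRF". Section 6.5.1 summarises the time on treatment and the amount of study drug given.

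Protocol 9.7 includes TEAEs that lead to stopping study drug(s) or to withdrawal among its safety tables and listings. Protocol 9.7.1.8 asks for an overview table in which "those TEAEs that led to study drug discontinuation, or dose interruption will be provided". SAP 8 expects no changes to the planned analyses.

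**The concern.** The study has one objective, the long-term safety of study drug(s). TEAEs that stop treatment are among its most informative results. The SAP covers such events for all study drugs in its overview row and its listing. When it breaks them down in a dedicated table, it narrows to one drug. It does the same for dosing.

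Two groups of subjects fall outside the dedicated table. Cohort C subjects take a comparator, so no event of theirs can lead to discontinuation of lenvatinib. Cohort B subjects who stop only the partner drug are left out for the same reason. For these subjects the events that ended treatment could be read only line by line. A reader of the table alone might take their absence as absence of events. Their comparator or partner dosing would have no listing.

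The SAP gives no reason for the narrower scope and does not record it as a change.

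**Working it through.** No arithmetic applies, because the plan states no figure here and the study is descriptive. The check sets each relevant output against the protocol's definition of study drug(s) and the three cohorts.

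**Count.** Of the 12 tables in SAP 6.5.2, 1 names a single drug; the other 11 do not. Of the 8 listings, 1 names a single drug; the other 7 do not.

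**Coverage, reading each title literally.**

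| SAP output | Drug named | Cohort A | Cohort B | Cohort C |
|---|---|---|---|---|
| Discontinuation table, 6.5.2 | lenvatinib | covered | only if lenvatinib is stopped | cannot appear |
| Dosing listing, 6.5.2 | lenvatinib | covered | lenvatinib part only | nothing to list |
| Overview row, 6.5.2 | study drug | covered | covered | covered |
| Listing of AEs leading to discontinuation, 6.5.2 | study drug | covered | covered | covered |
| Disposition summary, 6.2.2 | study drug | covered | covered | covered |
| Exposure summary, 6.5.1 | study drug | covered | covered | covered |

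**Are the other drugs foreseen?** Yes. Protocol 9.4.1 names sorafenib as the comparator in China and places those subjects in Cohort C. Protocol 9.4.1.5 gives interaction guidance for everolimus, pembrolizumab and sunitinib.

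**Is stopping one drug of a combination foreseen?** The Dose Modifications text of the protocol synopsis has the investigator judge causality, and whether to modify dosing, for one drug or both. Drug-by-drug decisions are therefore part of the design.

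**Are the data there?** Protocol 9.4.1 has the study drug(s) administered recorded in the CRF, which supports a dosing listing for all of them. The overview row and the AE listing already require a flag for TEAEs leading to study drug discontinuation. A table worded for study drug(s) would use the same flag.

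**Size.** SAP 5 expects about 50 subjects at first, possibly more later. Neither document says how many are in each cohort, so the number affected cannot be derived.

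**The case against.** The strongest reply is that the subject is already covered. Four outputs use general study-drug wording, so every relevant discontinuation is both counted and listed. Protocol 9.7.1.8 asks for the overview row, which the SAP provides. The protocol does not explicitly ask for a discontinuation table by preferred term or for a dosing listing. SAP version 2.0 deliberately cut the number of outputs. The shells, which SAP 12 places in a separate document, may already be wider. Version 2.0 is dated February 2024, and its authors may have known that few or no subjects were in Cohort C.

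Most of this stands, and it keeps the point small. It does not remove it. The SAP chose to include a dedicated table and a dosing listing, and as written each leaves out drugs that the protocol counts as study drug(s). If the shells are wider, the SAP text should match them. If the limit is deliberate, the SAP should say why.

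A reader might infer three stronger things that the documents do not support.

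- That discontinuations of partner or comparator drugs go unreported. They do not; see the coverage table.
- That Cohort C subjects in the denominator dilute the lenvatinib percentages. This would need columns that pool Cohort C with the others, and a known Cohort C share. SAP 4 does plan regional and all-subject summaries, but protocol 9.7.1.6 promises summaries by treatment group, SAP 6.3 allows a footnoted denominator, and no cohort mix is given. No dilution figure can be supported.
- That a wider dosing listing would supply the dose-reduction summaries promised in protocol 9.7.1.6. Those are a separate matter affecting lenvatinib as well, and a listing is not a summary.

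**Conclusion.** The point holds as a minor gap in coverage. One of 12 tables and one of 8 listings are narrower than the protocol's definition of study drug(s). Cohort C is outside both, and Cohort B is covered only for its lenvatinib component. What is missing is the event-level discontinuation summary and the dosing listing for non-lenvatinib drugs. No data or events are lost.

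This rests on three assumptions: the two titles mean what they say; the unseen shells do not already widen them; and stopping one drug of a combination counts as discontinuing study drug under the general wording, which is the natural reading but is not spelled out. The number of subjects affected is unknown and could be small.

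**What to change.** Retitle the table so that it covers TEAEs leading to discontinuation of study drug(s), and present it by treatment group as protocol 9.7.1.6 requires. Retitle the listing as study drug dosing, covering every study drug recorded in the CRF. If a lenvatinib-only section of the table is kept, footnote its denominator as lenvatinib-treated subjects, as SAP 6.3 allows. If the sponsor intends to keep the lenvatinib limit, state it and the reason in SAP 8.

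The cost is two titles, at most one footnote and minor shell work. Some cells for Cohorts B and C may be small. The documents point to no new data collection: protocol 9.4.1 already has study drug administration recorded, and the planned overview row already needs the discontinuation flag.

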6.5.3 Laboratory Values

Clinical laboratory tests including hematology, chemistry, and urinalysis will be performed per local standard of care or as clinically indicated. Laboratory values will not be collected in the eCRF, but any laboratory abnormalities that meet the definition of a TEAE (see protocol section 9.5.7.1) will be recorded on the Adverse Events eCRF. These will be summarized as TEAEs along with all other TEAEs.

6.5.4 Vital Signs

Vital signs measurements will be performed as per local standard of care or as clinically indicated. Only changes from screening vital signs findings that meet the definition of a TEAE will be recorded on the Adverse Events eCRF. These will be summarized as TEAEs along with all other TEAEs.

6.5.5 Physical Examinations

Physical examinations will be performed as per local standard of care or as clinically indicated. Only changes from screening physical examination findings that meet the definition of a TEAE will be recorded on the Adverse Events eCRF. These will be summarized as TEAEs along with all other TEAEs.

6.5.6 Electrocardiograms

Complete, standardized, 12-lead ECG recordings (if required) will be performed as per local standard of care. Only changes from screening ECG findings that meet the definition of a TEAE (see protocol section 9.5.7.1) will be recorded on the Adverse Events eCRF. These will be summarized as TEAEs along with all other TEAEs.

6.6 Other Analyses

Not Applicable

6.7 Exploratory Analyses

Not Applicable

7 INTERIM ANALYSES

No interim analyses are planned for this study.

8 CHANGES IN THE PLANNED ANALYSES

No changes to planned analyses are expected.

9 DEFINITIONS AND CONVENTIONS FOR DATA HANDLING

Statistical programming and analyses will be performed using SAS® (SAS institute, Inc., Cary, NC, USA), Version 9.4 or higher.

In general, missing or partial dates for adverse events will be imputed in order to assign treatment emergent status. The details on data handling will be provided in Analysis Data Model (ADaM) Specification Documents.

10 PROGRAMMING SPECIFICATIONS

The rules for programming derivations and dataset specifications are provided in separate documents.

11 STATISTICAL SOFTWARE

All statistical analyses will be performed using SAS v 9.4 or later. Statistical summaries will be prepared by Eisai or its designee.

12 MOCK TABLES, LISTINGS, AND GRAPHS

The study table, listing and graph (TLG) shells will be provided in a separate document, which will show the content and format of all tables, listings, and graphs in detail.

13 REFERENCES

Not applicable

